### 1.4.3 Risk Associated with Lack of Efficacy

With the administration of IFX-1 or placebo, no deterioration in health status is expected with respect to HS. Nevertheless, deterioration in HS can occur due to the fluctuating nature of the

---

disease. In case of a lack of efficacy with IFX-1 treatment, or in case of placebo treatment, subjects will continue to experience their typical HS symptoms.

Subjects who have a loss of response (see Definitions of Terms) during the Extension Period will have an optional visit 2 weeks later. Subjects who then have a loss of response at the subsequent (planned) visit will be discontinued from the study and will not switch to the non-responder schedule.

Subjects who experience WOAI (see Definitions of Terms) at 2 consecutive visits during the Extension Period will be discontinued from the study.

#### **1.4.4 Risk-Benefit Conclusion**

HS is a chronic inflammatory skin disease, which affects approximately 1% of the general population in the West, with women affected 2 to 5 times more commonly than men [21], and an average onset age of 23 years. This poorly understood disease is believed to be under-reported by those who suffer from it.

The disease is associated with significant morbidity. Given the pain and consequent physical impairment associated with the tender lesions that are symptomatic of this disease, it has been reported that health-related quality of life (HRQL) is lower in patients with HS than in patients with other dermatological diseases. Furthermore, a recent study estimated that up to 20% of patients with HS report the co-existence of depression, and patients with HS report a high level of stigmatization. Due to the significant physical and emotional burden of this disease, patients often aggressively seek treatment.

The level of disease severity strongly influences the approach to the treatment of HS. Subjects with moderate to severe HS (Hurley Stage II or III disease) will be included in this study. Subjects with Hurley Stage II disease exhibit recurrent inflamed nodules and abscesses, which often lead to sinus tracts and scarring that may not resolve with antibiotic therapy. Subjects with Hurley Stage III disease require preventive and medical therapy, and efficacy in severe HS was shown for adalimumab, infliximab, and acitretin [3].

It is hypothesized that treatment with IFX-1 could block the C5a-mediated inflammatory effect and thus reduce the pain and consequent physical impairment associated with the tender lesions of HS, and may even improve the disease status. During treatment with 9 weekly doses of IFX-1 in a proof-of-concept study in subjects with moderate to severe HS (IFX-1-P2.3), the AN count decreased, the HiSCR increased, and the Hidradenitis Suppurativa- Physician's Global Assessment (HS-PGA) indicated a shift from very severe to moderate disease. This dosing regimen was well tolerated and, as seen in the other Phase I and II studies, IFX-1 had a favorable safety profile.

In case of a lack of efficacy with IFX-1 treatment or in case of placebo treatment, subjects will continue to experience their typical HS symptoms, for which currently only limited treatment options are available.

The hypothesized benefit of treatment with IFX-1, therefore, outweighs the potential risks for the subjects participating in this study.

---

## 2 OBJECTIVES

### 2.1 Primary Objective

The primary objective of the study is to evaluate a dose-response signal of IFX-1 in subjects with HS according to the HiSCR at Week 16.

### 2.2 Secondary Objectives

The secondary objectives of the study are:

- To assess the efficacy of IFX-1 using additional outcome measures
- To assess the safety and tolerability of IFX-1
- To generate data for PK and PD modelling
- To assess patient-reported outcomes
- To evaluate the long-term efficacy and safety of IFX-1

## 3 STUDY DESIGN

### 3.1 Overall Design

This is a prospective, randomized, 2-period, placebo-controlled and double-blind (Main Period) and open-label (Maintenance Phase of Extension Period) multicenter study.

After establishing that the inclusion and exclusion criteria have been fulfilled at Screening (Sections 4.1 and 4.2), 175 subjects are planned to be randomized to receive double-blind treatment with IMP in 1 of 5 treatment cohorts in a ratio of 1:1:1:1:1.

Subjects who give informed consent for participation in the PK substudy will be sequentially included in the PK substudy.

Subjects will further be asked to consent to a photographic documentation of areas affected by HS. Subjects who consent will have photographs taken at prespecified times (Section 8.2.2.13).

An independent, unblinded Data Monitoring Committee (DMC) will be established to allow regular monitoring of the study data in order to detect and report early evidence of unanticipated harm to subjects (Section 13.3).

#### Main Period (16 Weeks)

For each cohort, the Main Period starts at Week 0 (Day 1, immediately before first administration of IMP) and consists of a 2-week Induction Phase (ends immediately after administration of IMP at Week 2) followed by a 14-week Maintenance Phase through Week 16 (ends immediately after administration of IMP at Week 16).

During the Main Period, IMP (IFX-1 or placebo) will be administered in 5 treatment cohorts: placebo, IFX-1 400 mg q4w, IFX-1 800 mg q4w, IFX-1 800 mg q2w, and IFX-1 1200 mg q2w, as summarized in Table 2.

The primary efficacy endpoint will be the percentage of subjects with a response on the basis of the HiSCR determined at Week 16, before administration of IMP (Section 8.2.2.2).

---

## PK Substudy in Main Period

A PK substudy will be conducted in approximately 50 of the 175 subjects participating in the Main Period. The subjects in Cohorts 1 to 5 will be sequentially included for participation in the PK substudy if consent for participation was given. The PK substudy assessments will be made on 2 visits during the Main Period, at Weeks 2 and 16.

### Extension Period (28 Weeks) – HiSCR Responders

Subjects from all cohorts who are HiSCR responders at Week 16 (response on the basis of HiSCR is defined in Section 8.2.2.2) will receive IFX-1 at a dose of 800 mg q4w, starting at Week 20 through Week 40. Subjects who have a loss of response (see [Definitions of Terms](#)) during the Extension Period will have an optional visit 2 weeks later. Subjects who then have a loss of response at the subsequent (planned) visit will be discontinued from the study.

A final visit at the study site for efficacy, PK, PD, and safety assessments will occur at Week 44. For subjects who discontinue early, a Post-Treatment Follow-Up visit will occur 3 months after the early discontinuation or when another HS therapy has been started, whichever occurs first. At the Post-Treatment Follow-Up visit the same parameters for efficacy, PK, PD and safety as at Week 44 or the early discontinuation visit will be assessed.

### Extension Period (28 Weeks) – HiSCR Non-Responders

Subjects from all cohorts who are HiSCR non-responders at Week 16 (response on the basis of HiSCR is defined in Section 8.2.2.2) will receive IMP during an Induction Phase (Weeks 18 and 19), followed by IFX-1 at a dose of 800 mg q2w during the Maintenance Phase from Week 20 through Week 40 (see also [Table 3](#)). Subjects who experience WOI (see [Definitions of Terms](#)) at 2 consecutive visits during the Extension Period will be discontinued from the study.

A final visit at the study site for efficacy, PK, PD, and safety assessments will occur at Week 44. For subjects who discontinue early, a Post-Treatment FUV will occur 3 months after the early discontinuation or when another HS therapy has been started, whichever occurs first. At the Post-Treatment Follow-Up visit the same parameters for efficacy, PK, PD and safety as at Week 44 or the early discontinuation visit will be assessed.

## 3.2 Study Sites and Number of Subjects

This multicenter study is planned to be conducted at approximately 50 sites in approximately 8 countries.

According to the sample size calculation (Section 10.2), 175 subjects are planned to be enrolled and randomized at Screening to 1 of 5 cohorts in the Main Period to ensure that approximately 145 subjects complete treatment with IFX-1 or placebo.

## 4 STUDY POPULATION

### 4.1 Inclusion Criteria

Subjects must meet all of the following criteria to be enrolled into the study:

Inclusion Criteria	Rationale	Criteria Checked at	
		Screening	Day 1
1. Male or female, $\geq 18$ years of age	Safety concern	X	
2. Written informed consent obtained from subject	Administrative	X	
3. Diagnosis of HS for at least 1 year	Effectiveness	X	
4. Moderate or severe HS, as indicated by HS lesions in at least 2 distinct areas, 1 of which must be at least Hurley Stage II or Stage III (Appendix 17.1)	Effectiveness	X	X
5. Stable HS for at least 2 months before Screening, as determined by the investigator through subject interview and review of medical history	Effectiveness	X	
6. Inadequate response to at least 3 months of oral antibiotics, or intolerance to antibiotics	Effectiveness	X	
7. Total abscess and inflammatory nodule count of $\geq 3$	Effectiveness	X	X

HS = hidradenitis suppurativa.

### 4.2 Exclusion Criteria

Subjects who fulfill any of the following criteria are not eligible to participate in the study:

Exclusion Criteria	Rationale	Criteria Checked at	
		Screening	Day 1
1. Body weight $< 60$ or $> 130$ kg	Safety concern	X	
2. Any other skin disease that may interfere with assessment of HS	Effectiveness	X	X
3. More than 20 draining fistulas	Safety concern	X	

Exclusion Criteria	Rationale	Criteria Checked at	
		Screening	Day 1
4. Prior treatment with adalimumab or another biologic product during the 24 weeks before Screening	Safety concern	X	
5. Prior treatment with IFX-1	Safety concern	X	
6. Subjects on permitted oral antibiotic treatment for HS (doxycycline or minocycline only) who have not been on a stable dose during the 28 days before Screening	Effectiveness	X	
7. Subject received systemic non-biologic therapy for HS with potential therapeutic impact for HS during the 28 days before Screening (other than permitted oral antibiotics)	Effectiveness	X	
8. Prior treatment with any of the following medications during the 28 days before Screening: a. Any other systemic therapy for HS b. Any iv anti-infective therapy c. Phototherapy (UVB or psoralen and UVA)	Effectiveness	X	
9. Prior treatment with any of the following medications during the 14 days prior to IMP administration: a. Analgesics (including opioids) for HS-related pain b. Prescription-only topical therapies for HS c. Oral anti-infectives for infections other than HS	Effectiveness	X	
10. History of moderate to severe heart failure (NYHA Class III or IV), cerebrovascular accident during the 24 weeks before Screening, history of malignancy except for successfully treated non-metastatic basal cell or squamous cell carcinoma or in situ carcinoma of the cervix	Safety concern	X	

Exclusion Criteria	Rationale	Criteria Checked at	
		Screening	Day 1

11. One of the following abnormal laboratory findings:
 
 
a. WBC < 2500/mm^3
 
b. Neutrophil count < 1000/mm^3
 
c. Serum creatinine > 3 × UNL
 
d. Total bilirubin > 3 × UNL
 
e. Alanine aminotransferase > 5 × UNL
 
f. Aspartate aminotransferase > 5 × UNL
 
g. Positive Screening test for HIV-1 or 2, or hepatitis B or C virus
 
 
For Canada only: One of the following abnormal laboratory findings:
 
 
a. WBC < 2500/mm^3
 
b. Neutrophil count < 1000/mm^3
 
c. Serum creatinine > 3 × UNL
 
d. Total bilirubin > 1.5 × UNL
 
e. Alanine aminotransferase > 2.5 × UNL
 
f. Aspartate aminotransferase > 2.5 × UNL
 
g. Positive Screening test for HIV-1 or 2, or hepatitis B or C virus
 
	Safety concern	X	

12. Chronic and/or recurring systemic infections, history of invasive infections with atypical pathogens (i.e., which normally do not cause invasive infection, such as listeriosis), or known primary immunodeficiency
	Safety concern	X	

13. Subject is judged to be in poor general health, as determined by the investigator based upon medical history, physical examination, laboratory safety and, a 12-lead ECG
	Safety concern		X

14. Female subjects of childbearing potential unwilling or unable to use a highly effective method of contraception (pearl index < 1%) such as complete sexual abstinence, combined oral contraceptive, vaginal hormone ring, transdermal contraceptive patch, contraceptive implant, or depot contraceptive injection in combination with a second method of contraception such as condom, cervical cap, or diaphragm with spermicide during the study and for at least 1 month after last administration of IMP. For France only: the methods of contraception are applicable during the study and for at least 3 months after last administration of IMP.	Safety concern	X	X
15. History of drug or alcohol abuse during the 24 weeks before Screening	Safety concern	X	
16. Pregnancy, as verified by a positive pregnancy test, or nursing woman	Safety concern	X	X
17. Evidence or suspicion that the subject might not comply with the requirements of the study protocol	Safety concern	X	
18. Any other factor which, in the investigator's opinion, is likely to compromise the subject's ability to participate in the study	Safety concern	X	
19. The subject is an employee or direct relative of an employee at the study site or sponsor	Administrative	X	
20. The subject is imprisoned or lawfully kept in an institution	Administrative	X	
21. The subject has participated in a clinical study during the 3 months before Screening, or plans to participate in a clinical study	Administrative	X	
22. For Denmark only: Hypersensitivity to any excipients of IFX-1	Safety concern	X	

ECG = electrocardiogram, HIV = human immunodeficiency virus, HS = hidradenitis suppurativa, IMP = investigational medicinal product, iv = intravenous, NYHA = New York Heart Association, UNL = upper normal limit, UVA = ultra-violet A, UVB = ultra-violet B, WBC = white blood cell count.

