### 5.8.1 Prior Therapy

Any prior treatment with phototherapy, laser-surgical therapy, or antibiotics (see Section 5.8.2.2) during at least the 3 months before Screening will be documented in the eCRF. Subjects must have been on a stable dose of doxycycline or minocycline during the 28 days before Screening (“as needed” dosing is not considered stable).

Any prior treatment with oral corticosteroids, immunosuppressive drugs, biologics, biosimilars, investigational treatment, any other systemic therapy for HS, any iv anti-infective therapy, analgesics (including opioids) for HS-related pain (see Section 5.8.2.3), prescription-only topical therapies for HS, and oral anti-infectives for infections other than HS during the 28 days before Screening will be documented.

Any biologic treatment for HS used previously, including details on reason for discontinuation will be documented.

All information on the use of prior medication will be recorded in the source documentation and in the eCRF.

Prior therapy should also include a detailed history of prior therapies used to treat HS.

All medications will be documented in the eCRF by verbatim name, dosing regimen, route of administration, start and end date of administration, and indication.

---

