### 5.8.3 Prohibited Therapy

The following therapies are prohibited for all subjects during the study:

- Phototherapy (UVB or psoralen and UVA)
- All biologic therapy with a potential therapeutic impact on the disease being studied including, but not limited to, the following:
  - Abatacept (Orencia®)
  - Anakinra (Kineret®)
  - Belimumab (Benlysta®)
  - Certolizumab pegol (Cimzia®)
  - Efalizumab (Raptiva®)
  - Etanercept (Enbrel®)
  - Golimumab (Simponi®)
  - Infliximab (Remicade®)
  - Natalizumab (Tysabri®)
  - Rituximab (Rituxan®)
  - Tocilizumab (Actemra®)
  - Ustekinumab (Stelara®)
- Any investigational agent
- Any other systemic medication for HS, including, but not limited to, antibiotics (except as specified in Section 5.8.2.2), methotrexate, cyclosporine, retinoids, and fumaric acid esters
- Oral or injectable corticosteroids
- Oral analgesics for HS not listed in Section 5.8.2.3
- Oral opioid analgesics for non-HS-related pain (for HS-related pain, see Section 5.8.2.3)
- New prescription topical therapies for HS
- Over-the-counter topical antiseptic washes, creams, soaps, ointments, gels, and liquids containing antibacterial agents to treat HS, not listed in Section 5.8.2
- Surgical or laser intervention for an HS lesion

---

The investigator should contact the sponsor if there are any questions regarding prior or concomitant therapy.

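### Systemic corticosteroids are barred on study for any indication, but the entry washout covers only use for HS, so a subject treated for another disease can reach Day 1 only 10 to 28 days off drug

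*Combined protocol and SAP*

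**What the plan says.** **On study.** Section 5.8.3 opens with "The following therapies are prohibited for all subjects during the study" and lists "Oral or injectable corticosteroids". That bullet names no indication, whereas several of its neighbours are limited to HS treatment or to pain unrelated to HS. Section 5.8.2.4 separately permits intralesional triamcinolone for an acutely painful lesion.

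**At entry.** In section 4.2, criterion 7 applies where "Subject received systemic non-biologic therapy for HS with potential therapeutic impact for HS during the 28 days before Screening", and criterion 8a covers "Any other systemic therapy for HS" over the same 28 days. No criterion names corticosteroids. The synopsis repeats this list, and the population rationale in section 1.3 keeps the same HS limit for systemic non-biologic therapy.

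**Recording.** Section 5.8.1 lists "Any prior treatment with oral corticosteroids, immunosuppressive drugs, biologics, biosimilars, investigational treatment" and further therapies from the 28 days before Screening as items to be documented. It does not make them exclusions.

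**Other therapies.** Criterion 4, "Prior treatment with adalimumab or another biologic product during the 24 weeks before Screening", does not depend on the indication. Nor do phototherapy (criterion 8c) or the 14-day analgesic washout in section 5.8.2.3.

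**The concern.** The on-study ban and the entry washout cover different sets of corticosteroid users. Use for a disease other than HS falls under the ban but not under the washout.

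This matters because section 1.1 counts corticosteroids among the treatments that may work in HS, and section 8.2.2.2 defines HiSCR relative to Day 1. If such a drug has just been withdrawn, the Day 1 counts may not reflect the subject's usual disease level. The baseline AN count is also a covariate in the primary model and a factor in the imputation model (section 10.5.1), and it enters the loss-of-response and WOAI rules (Definition of Terms). Section 1.3 says that the prior-therapy exclusions are there to make the population homogeneous.

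**Working it through.** **Inputs**
- Interval from Screening to first IMP: 10 to 28 days (section 7.1). The width, 28 − 10 = 18 days, agrees with the 18 days given in section 3.3.
- Washout under criteria 7 and 8a: 28 days before Screening, systemic therapy for HS only (section 4.2).
- Washout for corticosteroids taken for another disease: none.
- Stopping date: Screening. Section 5.8.3 applies during the study without giving a start day. The Definition of Terms has participation begin after consent is signed, so Screening is taken as the latest compliant stopping date.

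**Formula.** Minimum days off drug at Day 1 = washout before Screening + interval from Screening to first IMP.

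| Systemic corticosteroid use | Shortest interval | Longest interval |
|---|---|---|
| For HS (criteria 7 and 8a) | 28 + 10 = 38 | 28 + 28 = 56 |
| For another disease, stopped at Screening | 0 + 10 = 10 | 0 + 28 = 28 |
| Difference | 38 − 10 = 28 | 56 − 28 = 28 |
| Any indication, after the fix | 28 + 10 = 38 | 28 + 28 = 56 |

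**Could another provision supply the washout?**
- *Therapy reviews.* Section 7.1 has one review tied to the exclusion criteria and a separate one of chronic-disease therapy over the previous 3 months. The second should bring the use to light. Footnote (a) to the Schedules of Assessments updates therapy on Day 1 to confirm eligibility, and section 5.5 says that a subject found ineligible then should not be treated. Both depend on a criterion being failed, and none addresses this use.
- *Discretionary criteria.* Criterion 17, "Evidence or suspicion that the subject might not comply with the requirements of the study protocol", and criterion 18 are marked for Screening only. A subject who agrees to stop gives no obvious ground under 17. Criteria 2 and 13 (other skin disease, general health) can remove individuals. None of the four sets a time off drug.
- *Inclusion criterion 5.* Stable HS is required for the 2 months before Screening, when this subject was still on treatment, and it is not rechecked on Day 1.
- *Sponsor contact.* Section 5.8.3 adds "The investigator should contact the sponsor if there are any questions regarding prior or concomitant therapy". That offers advice but sets no window.
- *Per protocol set.* Section 10.3 removes major violations. A subject who stopped at Screening has committed none and stays in.

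**The case against.** The strongest reply is that nothing shows 10 to 28 days to be too short. The protocol gives no carry-over or withdrawal effect for corticosteroids, and criterion 9 accepts 14 days before IMP for prescription topicals, analgesics and oral anti-infectives. AN count and Hurley stage are rechecked on Day 1 (section 4.1). The HS limit also recurs in section 1.3, which fits a deliberate choice. And the sentence in section 1.1 that names corticosteroids also names immunosuppressive drugs, so a baseline-noise argument would reach methotrexate or cyclosporine taken for other diseases.

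Much of this stands. The size of any effect is unknown, and the Day 1 recheck does protect the minimum disease level, though not the time off drug. For methotrexate and cyclosporine, section 5.8.3 and the entry criteria share the same HS limit, so the two rules agree. Corticosteroids are where they differ, and the protocol gives no reason for the difference.

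Two stronger readings are tempting. A reader might infer that sites would not see such use. They should, through the chronic-disease review in section 7.1 and the Day 1 update; what is missing is a rule to apply. A reader might also infer that every corticosteroid taken for HS has a washout of at least 38 days. Criteria 7 and 8a say systemic, so an intralesional injection is outside that comparison.

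**Conclusion.** The gap is real and small. A subject who stops a systemic corticosteroid for another disease at Screening is compliant and, unless the investigator uses a discretionary criterion, eligible. That subject can have the HiSCR reference taken 28 days sooner after withdrawal than one treated systemically for HS. The consequence is some baseline noise in a probably small number of subjects. Neither that number nor the size or direction of any withdrawal effect is in the documents.

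A reader might go on to infer bias between cohorts, lost power or protocol violations. Randomization spreads such subjects over the cohorts without regard to treatment, no figure supports a power calculation, and a subject who stops breaks no rule.

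The conclusion rests on two readings: that the unqualified bullet in section 5.8.3 applies to any indication, and that the ban runs from Screening. If a site applied it only from Day 1, the time off drug could be less than 10 days. This is a low-cost improvement to consider, not a flaw that threatens the primary analysis.

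**What to change.** Add one item to exclusion criterion 8 in section 4.2 and to the same list in the synopsis: *d. Systemic (oral, intramuscular or intravenous) corticosteroids for any indication.* The existing window of 28 days before Screening then applies, and the minimum at Day 1 becomes 38 days whatever the indication.

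Leave local injections, including intralesional ones, out of the new item. Section 5.8.2.4 permits intralesional triamcinolone on study, and section 5.8.2.2 gives intralesional corticosteroid as an example of an intervention that marks antibiotic failure. Excluding recent local use would make entry stricter than conduct for the same treatment and would turn away part of the target population.

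The cost is two lines of text and a few more screen failures. A subject who can stop may be rescreened once (section 4.4) after the 28 days. No new data are needed, because section 5.8 already records all medication from the 3 months before Screening.

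Optionally, the corticosteroid bullet in section 5.8.3 could cross-refer to the triamcinolone allowed in section 5.8.2.4. That is a clarification only.

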	
 
• Any other factor which, in the investigator's opinion, is likely to compromise the subject's ability to participate in the study
 
• The subject is an employee or direct relative of an employee at the study site or sponsor
 
• The subject is imprisoned or lawfully kept in an institution
 
• The subject has participated in a clinical study during the 3 months before Screening, or plans to participate in a clinical study
 
• For Denmark only: Hypersensitivity to any excipients of IFX-1
 

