Investigational medical product(s) [IMP], dose, and mode of administration	
IFX-1 is provided in 10 mL vials containing 100 mg IFX-1 and will be infused over a period of 30 to 60 minutes (min) via an intravenous (iv) line.
 
Placebo is provided in 10 mL vials containing sodium chloride, sodium phosphate, and Polysorbate 80. The placebo vials and content have the same appearance as the IFX-1 vials and additives.
 
Main Period (16 weeks): For each cohort, the Main Period starts at Week 0 (Day 1, immediately before first administration of IMP) and consists of a 2-week Induction Phase (ends immediately after administration of IMP at Week 2) followed by a 14-week Maintenance Phase through Week 16 (ends immediately after administration of IMP at Week 16).
 
Cohort 1 (placebo):
 
 
• Induction Phase: placebo at Weeks 0 (Days 1 and 4), 1, and 2
 
• Maintenance Phase: placebo at Week 4 and every other week through Week 16
 
 
Cohort 2 (IFX-1 400 mg q4w):
 
 
• Induction Phase: IFX-1 400 mg at Week 0 (Days 1 and 4), followed by placebo at Weeks 1 and 2
 
• Maintenance Phase: IFX-1 400 mg at Week 4, followed by alternating infusions every other week of placebo or 400 mg IFX-1 through Week 16
 
 
Cohort 3 (IFX-1 800 mg q4w):
 
 
• Induction Phase: IFX-1 800 mg at Weeks 0 (Days 1 and 4) and 1, followed by placebo at Week 2
 
• Maintenance Phase: IFX-1 800 mg at Week 4 followed by alternating infusions every other week of placebo or IFX-1 800 mg through Week 16
 
 
Cohort 4 (IFX-1 800 mg q2w):
 
 
• Induction Phase: IFX-1 800 mg at Weeks 0 (Days 1 and 4), 1, and 2
 
• Maintenance Phase: IFX-1 800 mg at Week 4 followed by IFX-1 800 mg every other week through Week 16
 

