*Meningitis/meningococcal septicemia:* current data do not suggest that subjects treated with IFX-1 are at significantly increased risk of infection with *N. meningitides* and to date, no cases of meningitis or meningococcal septicemia have been reported in clinical studies with IFX-1. Therefore, mandatory vaccination or concomitant broad spectrum antibiotic treatment is not warranted based on the mode of action for IFX-1. However, until a larger number of subjects have been exposed to IFX-1, investigators should be vigilant for signs of *N. meningitides* infection. See Section [5.6](#) for the procedures to be followed in case of meningitis/meningococcal septicemia.

*Anaphylactic reactions and acute systemic allergic hypersensitivity:* because IFX-1 is an antibody/protein, a general risk for anaphylactic reactions and acute systemic allergic hypersensitivity exists. Subjects who are included in this study are treated with IFX-1 at the study site so that adequate treatment and care is available in case of an anaphylactic reaction. To date, no anaphylactic reactions have been reported after administration of IFX-1 in clinical Phase I and II studies. See Section [5.6](#) for the procedures to be followed in case of anaphylactic reactions and acute systemic allergic hypersensitivity.

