### 5.1 Investigational Medicinal Product

#### 5.1.1 IFX-1

IFX-1 is a monoclonal anti-human C5a immunoglobulin as active pharmaceutical ingredient, which is formulated in a phosphate buffered saline and Polysorbate 80.

IFX-1 will be supplied in 10 mL glass vials at a concentration of 10 mg/mL (i.e., 100 mg per vial) for iv administration and will have the following composition:

Ingredient	Strength
IFX-1	10 mg/mL
Sodium chloride	150 mM
Sodium phosphate	10 mM
Polysorbate 80	0.05%

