**Fax: [name]**  
**QLS\[contact]**

### **9.3 Adverse Events of Special Interest**

An AESI is an AE of scientific and medical concern specific to the sponsor's product or program, for which ongoing monitoring and rapid communication by the investigator to the sponsor could be appropriate. Such an event might require further investigation in order to characterize and understand it.

For this study, the following AEs are defined as AESIs:

- Acute systemic hypersensitivity reaction
- Meningitis
- Meningococcal septicemia
- Invasive infection

All AESIs will be recorded and reported as SAEs, and subject narratives will be generated.

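### Excipient hypersensitivity is a mandatory exclusion in Denmark only, although every infusion in every country contains the same excipients and no reason for the difference is given

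*Combined protocol and SAP*

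**What the plan says.** Section 4.2 lists 22 exclusion criteria. The last, "Hypersensitivity to any excipients of IFX-1", checked at Screening with a safety rationale, is limited to one country. The synopsis carries it in the same form: "For Denmark only: Hypersensitivity to any excipients of IFX-1".

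Section 5.1.1 describes IFX-1 as "formulated in a phosphate buffered saline and Polysorbate 80". For the comparator the synopsis states: "Placebo is provided in 10 mL vials containing sodium chloride, sodium phosphate, and Polysorbate 80". The composition tables in Sections 5.1.1 and 5.1.2 give identical excipient strengths.

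Other hypersensitivity provisions apply in all countries. Section 1.4.2 says that, because IFX-1 is a protein, "a general risk for anaphylactic reactions and acute systemic allergic hypersensitivity exists". Section 9.3 lists "Acute systemic hypersensitivity reaction" among the events of special interest, to be reported as SAEs. Section 6.2.2 requires treatment to stop after an anaphylactic or other serious allergic reaction, and Section 5.6 stops the infusion and further dosing after a severe acute systemic reaction.

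**The concern.** The protocol treats a known excipient allergy as serious enough for mandatory exclusion, but only at Danish sites. The formulation does not differ by country, so nothing in the documents ties the hazard to Denmark. Elsewhere the plan acts in a defined way once a reaction has occurred, but has no mandatory screen for a subject already known to be predisposed.

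A reaction in such a subject could have been avoided. The criterion is already written, so the gap is one of scope. An investigator elsewhere who sees the country label may also take it that the question need not be asked.

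**Working it through.** The protocol gives no figure on this point to reproduce. The check sets the relevant sections side by side and counts infusions by hand.

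**1. Is there another criterion that names this allergy?** None of the 7 inclusion criteria (Section 4.1) or the other 21 exclusion criteria (Section 4.2) mentions allergy or hypersensitivity to the study product or its components. Criterion 13 concerns poor general health. Criterion 18 lets the investigator exclude for any other factor likely to compromise participation. It also has a safety rationale and applies in all countries, but it is discretionary and does not mention allergy.

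**2. Does exposure differ by country or arm?**

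| Excipient | IFX-1 (5.1.1) | Placebo (5.1.2) |
|---|---|---|
| Sodium chloride | 150 mM | 150 mM |
| Sodium phosphate | 10 mM | 10 mM |
| Polysorbate 80 | 0.05% | 0.05% |

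All five cohorts are exposed, and no country variant of the formulation is described.

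**3. Is criterion 22 like the other national variants in Section 4.2?** The Canadian variant tightens some laboratory limits that exist everywhere (for example, bilirubin 1.5 instead of 3 times the upper normal limit). The French variant lengthens a contraception period that exists everywhere (3 months instead of 1). Criterion 22 has no base rule elsewhere.

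**4. How many infusions are scheduled?** Taking the placebo cohort from the synopsis:

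- "Induction Phase: placebo at Weeks 0 (Days 1 and 4), 1, and 2": 4 infusions.
- "Maintenance Phase: placebo at Week 4 and every other week through Week 16": Weeks 4, 6, 8, 10, 12, 14 and 16, so 7 infusions.
- Main Period total: 4 + 7 = 11. Table 2 shows the same number of visits in every cohort.
- Extension Period, Table 3: 6 infusions for Week 16 responders and 14 for non-responders. Scheduled totals are 11 + 6 = 17 and 11 + 14 = 25.

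These are scheduled maxima. The stopping provisions in Sections 5.6 and 6.2.2 would cut them short after a serious reaction.

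**5. How large could the effect be?** The criterion binds in 1 of approximately 8 countries (Section 3.2); this is not a share of subjects. The documents do not say how many candidates have a known excipient allergy. Assuming 0 to 1 of 175, the share randomized is 0 to 1/175 = 0.6%. One event in a planned cohort of 35 would be 1/35 = 2.9% of that cohort.

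**The case against.** The best defence is that the protocol does not oblige any site to enrol such a subject. Criterion 18 is available everywhere, and a known allergy to a component of every infusion plausibly falls within it. The country label limits criterion 22 only and does not disapply criterion 18. That stands: the gap is between mandatory and discretionary exclusion, and it would be too much to say that the plan admits these subjects.

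Three stronger readings are tempting, and the documents do not support them.

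- *That the protocol itself recognises an excipient risk in all countries.* Section 1.4.2 attributes the hypersensitivity risk to IFX-1 being an antibody, and reports no anaphylactic reactions to date.
- *That an allergic subject would go through all 11 Main Period infusions.* A severe reaction stops dosing. Subjects must also stay at least 30 minutes after each of the first two infusions of an Induction Phase (in France, at least 60 minutes after every infusion in that phase). These measures act only after exposure and do not replace screening, but they make 11 an upper bound.
- *That excipient reactions would distort the safety comparison.* The excipients are common to all arms and allocation is randomized 1:1:1:1:1, so the risk is balanced in expectation and any effect is noise. Listing an event as of special interest does not attribute it to IFX-1; causality is assessed separately (Section 9.1.2). Safety is a secondary objective (Section 2.2).

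It may also be said that national variations are routine and that this one may come from a national authority. The documents do not say so, and such an origin would not explain why a rule the protocol classes as a safety matter stops at one border. The Investigator's Brochure and the IMP manual may contain precautions, but they are not part of the documents reviewed.

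**Conclusion.** The point holds as an unexplained inconsistency of scope. The same hazard, in the same formulation, leads to mandatory exclusion in one country and to investigator discretion in the others. The result is a small, avoidable safety risk. Its size rests on the assumption of 0 to 1 affected subjects among 175, and the lower end of that range is no effect at all. Nothing here bears on the HiSCR dose-response test, its power or the validity of the randomized comparison. The case for acting is that the sponsor's own criterion already exists and extending it would cost little.

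**What to change.** Reconcile the scope of criterion 22 with the common formulation (Sections 5.1.1 and 5.1.2) and the trial-wide hypersensitivity provisions (Sections 1.4.2, 5.6, 6.2.2 and 9.3). Either remove the country restriction in Section 4.2 and the synopsis, so that the sponsor's existing criterion applies in all countries, or state why the concern is confined to Denmark.

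If the restriction is removed, the medical-history wording should be aligned too. Section 7.1 asks for history over the 6 months before Screening, Section 8.1.2 for a complete history, and neither mentions allergies, so an older reaction could be missed.

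The cost is more than deleting three words in two places. A change that may affect subjects' safety needs renewed ethics and authority approval (Section 11.4), though it can be bundled with another amendment. No new test is needed, and at most a very few subjects would be excluded.
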